6.2 Standard Dose

Subjects randomized to the favipiravir + SOC arm will be administered loading doses of 1800 mg BID (Ideally 12 hours apart but 10–16 hours is allowed) on Day 1, and then maintenance dosing of 1000 mg twice daily BID (Ideally 12 hours apart but 10–16 hours is allowed) on Days 2–14 beginning 24 hours after the first dose. Day 1 is deemed to be the first 24 hours after enrollment into the study, with time 0 (time of first dose) occurring as soon as possible after the subject's eligibility has been confirmed.

An exception to the above maintenance dose will be made for those subjects entering the study with a Child-Pugh liver impairment of grade A who will receive favipiravir 800 mg BID on Days 2 through 14.

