#### **3.3. General Methods**

All data listings that contain an evaluation date will contain a relative study day (Rel Day). Pre-treatment and on-treatment study days are numbered relative to the day of the first dose of study medication which is designated as Day 1. The preceding day is Day -1, the day before that is Day -2, etc.

All output will be incorporated into Microsoft Word, or Adobe Acrobat PDF files, sorted and labeled according to the International Council for Harmonisation (ICH) recommendations, and formatted to the appropriate page size(s).

Tabulations will be produced for appropriate demographic, baseline, efficacy, PK, and safety parameters. For categorical variables, summary tabulations of the number and percentage of subjects within each category (with a category for missing data) of the parameter will be presented along with 2-sided 90% confidence intervals (CIs). For continuous variables, the number of subjects, mean, median, standard deviation (SD), minimum, and maximum values will be presented, as well as 2-sided 90% CIs. Time-to-event data will be summarized using Kaplan-Meier methodology using 25th, 50th (median), and 75th percentiles with associated 2-

sided 90% CIs, as well as percentage of censored observations. Where appropriate, p-values will be reported.

Assuming raw or derived variables are to 'x' decimal places, the data will be presented as follows:

- Range to x decimal places
- Mean and median to (x+1) decimal places
- SD to (x+2) decimal places
- (x+2) should not be greater than 4 decimal places
- percentages may be calculated without a decimal place or with (x+1) decimal place

Formal statistical hypothesis testing will be performed on the primary and secondary efficacy endpoints as described in [Section 4](#) with all tests conducted at the 2-sided, 0.10 level of significance.

Data will be presented by subject and summarized by treatment group.

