### **3.5. Baseline Definitions**

For all analyses, baseline will be defined as the most recent measurement prior to the first administration of study drug for patients on favipiravir. For patients on SOC, baseline will be defined as the closest (either before or after) measurement to randomization.

For the purpose of time-to-event analyses, treatment start date is used as the origin point for patients on favipiravir, while randomization date is used for patients on SOC.

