## 3.11. Visit Windows

It is expected that all visits should occur according to the protocol schedule. However, analysis visits will be derived based on study day for all by-visit summaries and analyses. Analysis visit designations are detailed in [Table 3-1](#).

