### **4.3. Efficacy Evaluation**

#### **4.3.1. Analysis of the Primary Efficacy Endpoint**

The primary endpoint of time to viral clearance will be analyzed with the log-rank test for treatment difference based on a two-sided alpha-level of 0.10 and summarized using Kaplan-Meier methodology. The time to viral clearance (in days) is defined as the time of Negative or Lower Limit of Quantification (LLOQ) results (without any quantitative results after that) as measured by PCR for SARS-CoV-2 via scheduled nasopharyngeal and oropharyngeal swab samples minus the date of first dose + 1.

Subjects who have no evidence of viral clearance will be censored at the time of the last PCR measurement with the following conditions:

- Patients whose symptoms worsen (defined as an increase of  $\geq 1$  point on the 6-point Ordinal Scale from baseline) on the day of the last PCR measurement, or who die will be censored at Day 29,
- Patients who are lost to follow-up will be censored on the day of the last PCR measurement.

The median time to viral clearance will be estimated based on the Kaplan-Meier estimator; additional summary statistics will be presented, including the 25th and 75th percentiles, 90% CIs (the log-log transformation) on the median and other percentiles and proportion of censored subjects. Viral clearance rates at Days 3, 8, 11, 15, and 29 will also be presented.

The analysis of the primary efficacy endpoint will be done using the ITT population.

The primary analysis will be supplemented with a sensitivity analysis, using a stratified log-rank test, where the treatment difference based on a two-sided alpha-level of 0.10 will be summarized and stratified by disease severity.

The analysis will also be repeated by the dexamethasone usage subgroup, where patients will be categorized as having received dexamethasone if they received it at any time prior to the last viral clearance assessment.

Kaplan-Meier curves will be provided for the overall ITT population. By-subject data listings of viral clearance data will also be provided.

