#### 4.3.2.6. Duration of Supplemental Oxygen, Non-Invasive Ventilation, Mechanical Ventilation, ECMO, Hospitalization, and Time in ICU

The total duration (in days) of any respiratory assistance (supplemental oxygen, non-invasive ventilation, mechanical ventilation, ECMO), hospitalization, and ICU will be analyzed using an ANCOVA model, investigating the difference in means between the treatment groups. The difference in mean durations between treatment groups will be provided, along with 90% CI. All durations are counted from randomization. In addition, the total time on any ventilation assistance (non-invasive/mechanical ventilation, ECMO), and either mechanical ventilation or ECMO will be analyzed using an ANCOVA model as above.

The exact duration will be counted. But, it was initiated prior to study enrollment, duration will be calculated from treatment start date for patients on favipiravir and randomization date for patients on SOC. The maximum value of these durations will not exceed 60 days

The analyses above will be performed using the ITT population.

Box plots for the total duration of any respiratory assistance and hospitalization will be provided by treatment group. By-subject data listings for each parameter will also be provided.

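### Time zero is first dose for favipiravir but randomisation for SOC, so a dosing delay past midnight shortens only favipiravir times and tilts the primary log-rank test toward favipiravir

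*SAP*

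**What the plan says.** SAP 3.5 fixes the origin for all time-to-event analyses: "treatment start date is used as the origin point for patients on favipiravir, while randomization date is used for patients on SOC". The same section makes baseline asymmetric. It is the last pre-dose value for favipiravir, but "For patients on SOC, baseline will be defined as the closest (either before or after) measurement to randomization".

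Other sections do not fit together with this rule:

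- SAP 4.3.1 computes the primary endpoint as the date of the clearing swab "minus the date of first dose + 1". SOC patients have no such date.
- SAP 3.3 states that "study days are numbered relative to the day of the first dose of study medication which is designated as Day 1", and SAP 3.11 that "analysis visits will be derived based on study day for all by-visit summaries and analyses". Neither gives a rule for SOC.
- Protocol 6.2, like 7.2, ties the grid to enrolment: "Day 1 is deemed to be the first 24 hours after enrollment into the study".
- SAP 4.3.2.6 first says "All durations are counted from randomization". For anything under way before enrolment it then says "duration will be calculated from treatment start date for patients on favipiravir and randomization date for patients on SOC". Protocol 5.1 admits only patients already in hospital, so for length of hospitalisation the exception always applies.

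Protocol 7.1 places randomisation before the first dose. The dose is to follow promptly once eligibility is established, with no stated time limit. The only planned sensitivity analysis of the primary endpoint is a log-rank test stratified by disease severity, which keeps the split origin.

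**The concern.** Only the favipiravir arm can have a gap between randomisation and the start of its clock. If that gap crosses midnight, the lost days come off favipiravir times and stay in SOC times, so the error can only favour favipiravir. Protocol 9.1 makes a significant primary result the proof of concept. The ITT population was chosen to preserve the randomised comparison, and an arm-specific origin set after randomisation works against that. A patient randomised to favipiravir but never dosed belongs to ITT yet has no time zero, although few such patients are expected. Secondary p-values are descriptive, so the primary endpoint carries the main consequence.

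**Working it through.** **The plan's own figure.** Inputs from SAP 3.1: medians 4 and 11 days, two-sided alpha 0.10, power 90%, 15 days of observation.

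- Hazard ratio = 4/11 = 0.364.
- Exponential clearance by Day 15: 1 − 2^(−15/4) = 92.6% and 1 − 2^(−15/11) = 61.1%; mean 76.9%.
- Freedman: (1.645 + 1.282)² × (1.364/0.636)² = 39.3 events, so N = 51.2.
- Schoenfeld: 34 events, so N is about 44.

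The stated 50 is close to the Freedman result. The origin rule does not affect the sample size.

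**How a day is lost.** Both patients are randomised on date D; the favipiravir patient is dosed on D+1.

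- *Swabs timed from enrolment.* Both are negative on D+7. SOC time = 7 − 0 + 1 = 8 days; favipiravir time = 7 − 1 + 1 = 7 days. The infection course is the same but the recorded times differ.
- *Swabs timed from each arm's own origin.* The favipiravir swab moves to D+8, so its time is 8 − 1 + 1 = 8 days. The recorded times match, but the favipiravir patient has had one more day in which to clear.

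**Null simulation.** No drug effect; 25 per arm; log-rank at two-sided 0.10, so 5% nominal in each direction. Clearance is exponential or Weibull (shape 1.5) with median 11 days. Swabs fall on Days 3, 8, 11, 15 and 29, either exactly or uniformly within the allowed windows. There are 20,000 replicates per scenario (Monte Carlo SE about 0.15-0.35 points). The 1-day lag is an assumption. Ranges span both distributions and both visit-timing assumptions.

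False favipiravir wins under the SAP rule:

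| Favipiravir arm delayed 1 day | Swabs from own origin | Swabs from enrolment |
|---|---|---|
| 10% | 4.9-5.6% | 6.0-7.8% |
| 20% | 5.7-6.0% | 6.7-10.9% |
| 50% | 6.4-7.6% | 9.7-24.7% |
| 100% | 8.3-10.8% | 15.7-56.3% |

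The upper ends of the last column need exact visit days. With swabs from own origin, total two-sided error is 10.4-10.9% (half delayed) and 11.3-13.0% (all delayed).

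A second set of runs (10,000 per scenario, Weibull shapes 1 and 2, exact visit days) gave 4.6-5.3% with no delay. With half delayed it gave 6.6-8.2% (own origin) and 18.6-28.9% (enrolment).

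**Testing the remedies.**

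- Common origin and common swab days: 4.9-5.5% in each direction.
- Origin moved to randomisation while favipiravir swabs stay timed from first dose: false losses of 7.5-13.9% (half delayed) and 10.6-38.7% (all delayed).
- Interval-censored Weibull likelihood-ratio test from randomisation, swabs timed from first dose: 5.5-5.6% wins and 5.2-5.8% losses. This used 3,000 replicates (SE about 0.4), exact visit days and a correctly specified model.

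**The case against.** The strongest reply concerns size. Protocol 6.2 puts both loading doses in Day 1 and allows 10 hours as the shortest gap. If Day 1 runs 24 hours from enrolment, the first dose is due within 24 − 10 = 14 hours. That makes delay in the whole arm implausible. As an illustration, with randomisation uniform between 08:00 and 20:00 and a lag uniform up to 6 to 14 hours, about 3-30% of patients would cross midnight. Runs with the protocol's swab windows and a discharge swab (4,000 replicates, SE about 0.35-0.5) gave 5.2-6.6% false wins at 10-30% delayed with dose-timed swabs. With enrolment-timed swabs they gave 5.8-8.5%, and 9.3-10.6% with half delayed. Under the planned 4 v 11 day effect, power moves only from 94% to 97% (half delayed, dose-timed swabs, constant hazard). The trial is exploratory.

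Much of this stands: the largest figures in the table are not the likely ones. It does not remove the defect. A 14-hour limit is inferred, not stated, and still lets any patient randomised after 10:00 cross midnight. The synopsis instead counts Day 1 from the start of therapy, which removes that limit. The power figure does not bear on false wins when the drug has no effect.

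A second reply, also correct, is that moving the origin alone could do more harm than the present rule. The fix has to allow for that. Further, the protocol starts time to clinical recovery at initiation of study treatment, so a randomisation origin is a change to be declared.

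**Conclusion.** The rule is wrong as written and should be fixed. The direction is certain: any date-crossing lag favours favipiravir. The size depends on a lag the documents do not give. It is nil with same-date dosing, close to nominal if about 10% are delayed and swabs follow first dose, and material if delays are common or swabs are timed from enrolment. These figures assume a 1-day lag, a median of 11 days in both arms and no drug effect. The main simulation leaves out the discharge swab and the Day 29 censoring for death or worsening. The baseline asymmetry is a real inconsistency, but the direction of any bias from it cannot be determined.

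**What to change.** - Use the randomisation date as time zero in both arms in SAP 3.5, 4.3.1, 4.3.2.2 to 4.3.2.4, 4.3.2.6 and 4.3.2.8. Never-dosed ITT patients then have an origin.
- In the same change, number study days (3.3), swab days and analysis windows (3.11) from randomisation in both arms.
- If favipiravir swabs were in fact timed from first dose, use an interval-censored comparison from randomisation instead. Do not move the origin alone.
- Put the randomisation date into the 4.3.1 formula and delete the arm-specific exception in 4.3.2.6.
- Define baseline in both arms as the last value before randomisation. Protocol 7.1 already lists the baseline assessments ahead of that step. A patient whose only pre-dose value came after randomisation would lose a baseline.
- Report the distribution of the randomisation-to-first-dose lag.
- Keep the first-dose date for exposure and for onset of favipiravir treatment-emergent adverse events.
- List the changes in SAP 5, including the new origin for time to clinical recovery.

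The cost is SAP wording, revised date derivations and possibly one interval-censored analysis. Randomisation and dosing dates are already captured, so no patients or visits are added. If dosing was delayed, the favipiravir estimate will be slightly less favourable.

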### **3.6. Methods of Pooling Data**

Efficacy data will be pooled across study sites for analysis.

### **3.7. Adjustments for Covariates**

For the analyses of durations of supplemental oxygen, non-invasive/mechanical ventilation, Extracorporeal Membrane Oxygenation (ECMO), hospitalization, and ICU, baseline SpO2 level will act as a covariate in all analysis of covariance (ANCOVA) models. Disease severity, as defined in [Section 1.2.2](#), will be accounted for in all efficacy analyses. Other factors may be accounted for if deemed relevant.

### 3.8. Subpopulations

Subgroup analyses on dexamethasone usage (Yes/No) will be performed on the primary efficacy analyses, as well as on select secondary efficacy analyses. Other subgroups of interest may be analyzed for exploratory purposes.

### 3.9. Withdrawals, Dropouts, Loss to Follow-up

Subjects who are withdrawn or discontinued from the study will not be replaced.

### 3.10. Missing, Unused, and Spurious Data

#### 3.10.1. Efficacy Data

Should missing data occur for time-to-event endpoints, such subjects will be included in the log-rank analysis as censored observations as specified in Section 4.3.1.

Missing clinical outcome data for secondary efficacy endpoints (other than time-to-event) will be handled by a multiple imputation model that contains the following variables: baseline and post-baseline parameter values, and disease severity, stratified by treatment group. Imputation of missing data will be conducted under a working assumption of missing at random (MAR), meaning that the propensity for a data point to be missing is not related to the missing data, but it is related to some of the observed data.

The imputations will be performed for post-baseline visits. The Fully Conditional Specification (FCS) method will be used, given its natural handling of both ordinal and nominal variables (Liu & De 2015). Predicted Mean Matching (PMM) (using a linear prediction model to obtain predicted values and  $k=5$  for randomly drawing from  $k^{\text{th}}$  nearest observed values to the predicted value) will be implemented under FCS (Schenker & Taylor 1996). One hundred (100) datasets will be imputed in order to estimate the treatment effect, where the median value across the imputed datasets will be used for subjects with missing endpoints.

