#### 4.3.2. Analysis of Secondary Efficacy Endpoints

##### 4.3.2.1. Analysis of Clinical Status via the Study-Specific 6-point Ordinal Scale

The first secondary endpoint of clinical status as measured by the study-specific 6-point ordinal scale at Day 15 will be analyzed by fitting a cumulative odds model, using the most appropriate approach. Clinical status will be modelled as the dependent variable (ordered from 1 to 6, as defined in [Section 1.2.6.1](#)), and treatment group and disease severity as independent variables; other factors may be added for exploratory purposes. Subjects with missing Day 15 data will have their clinical status imputed in the following manner:

- 1) If patients were discharged prior to Day 15, then their clinical status will be imputed to 'Not Hospitalized' at Day 15
- 2) If patients died prior to Day 15, then their clinical status will be imputed to 'Death' at Day 15
- 3) If there is no evidence of hospital discharge or death, clinical status at Day 15 will be imputed using the multiple imputation method described in [Section 3.10.1](#)

The odds ratios and their 90% CI will be provided. As described in [Section 3.2](#), a test at the two-sided alpha level of 0.10 will be performed for descriptive purposes.

Longitudinal analysis of the 6-point scale over time at each visit will be performed in a similar manner. Clinical status will be modelled as the dependent variable and treatment group, disease severity, visit, and the visit/treatment group interaction term as independent variables. The overall treatment odds ratio and their 90% CI will be provided, along with by-visit odds ratios and 90% CI.

Analyses using the study-specific 6-point scale will be done using the ITT population.

The analysis will also be repeated by the dexamethasone usage subgroup, where patients will be categorized as having received dexamethasone if they received it at any time prior the Day 15 analysis visit assessment.

Stacked bar charts over time will be generated to graphically display the proportion of patients in each level of the 6-point scale by treatment group for the ITT population.

By-subject data listings will be provided.

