##### 4.3.2.3.1. Respiratory Progression

The frequency of respiratory progression as assessed up to Day 29 will be tabulated by treatment group. Respiratory progression is defined as:

SpO2  $\leq 94\%$  on room air or PaO2/FiO2 < 300 mmHg, and

- a. Requirement for supplemental oxygen, or
- b. More advanced ventilator support

The treatment effect will be analyzed via generalized linear mixed models using SAS PROC GLIMMIX, with respiratory progression (Yes/No) as the dependent variable, and treatment group, disease severity, age (in years), and visit as independent variables. Least-squares means of the treatment group effect on the logit scale (difference on the log odds) will be presented, along with a 90% CI and a descriptive p-value from a two-sided alpha-level test.

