#### 4.3.2.5. Reduction in Oxygen/Ventilation Requirements

The frequency of requirement for any supplemental oxygen or ventilation (non-invasive, mechanical, or ECMO), as assessed daily up to 29 days and on Day 45 and 60, if possible, will be analyzed in a similar fashion as respiratory progression in [Section 4.3.2.3.1](#).

In addition, the frequency of requirement for any ventilation requirement (non-invasive, mechanical or ECMO) and either mechanical ventilation or ECMO will be analyzed in the same manner as above.

The analyses on oxygen/ventilation requirements will be performed using the ITT population.

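### SAP 3.10.1 imputes missing secondary data with no exception for death, so respiratory progression and oxygen/ventilation status after death could be filled in from same-arm survivors

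*SAP*

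**What the plan says.** SAP 3.10.1 gives the general rule: "Missing clinical outcome data for secondary efficacy endpoints (other than time-to-event) will be handled by a multiple imputation model". The imputation model contains "baseline and post-baseline parameter values, and disease severity, stratified by treatment group", and "The imputations will be performed for post-baseline visits". The method is fully conditional specification with predictive mean matching on the 5 nearest observed values, 100 imputed datasets, "where the median value across the imputed datasets will be used for subjects with missing endpoints". Neither the rule nor the list of model variables mentions death.

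Two later sections do have a death rule for a non-time-to-event endpoint:

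- SAP 4.3.2.1, Day 15 ordinal scale. Among subjects with missing Day 15 data: "If patients died prior to Day 15, then their clinical status will be imputed to" the Death category. Multiple imputation is kept for subjects with no evidence of discharge or death. The longitudinal model of the same scale is only said to be done similarly.
- SAP 4.3.2.1.1, second sensitivity analysis. Once a subject has died, later timepoints receive no contribution from that subject.

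Two sections have none:

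- SAP 4.3.2.3.1: "The frequency of respiratory progression as assessed up to Day 29 will be tabulated by treatment group". The treatment effect comes from a generalized linear mixed model of a yes/no outcome with visit as a factor.
- SAP 4.3.2.5: requirement for oxygen or ventilation, "as assessed daily up to 29 days and on Day 45 and 60, if possible", analysed in the same way as respiratory progression.

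Protocol 9.6 lists worst-value assignment among the methods for missing clinical outcome data. The SAP does not take it up, and SAP Section 5 does not list that as a change.

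**The concern.** A subject who has died has no oxygen requirement to recover. Missing at random assumes that a value exists but was not observed, and that assumption has no meaning here. If the general rule is applied to these two endpoints, the donors for a dead subject's Day 21 or Day 29 status can only be subjects in the same arm who were alive and observed at that visit. By then many of them will be off support.

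The endpoints are meant to describe respiratory failure, and protocol 9.1 places reduction in oxygen/ventilation requirements among the key secondary endpoints that inform a Phase 3 trial. An arm with more deaths would have more of its values replaced by survivors' values.

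**Working it through.** **Does the general rule reach deaths?** SAP 4.3.2.1 lists subjects who died before Day 15 under missing Day 15 data, and needs a specific instruction to keep them out of the imputation. That shows status after death being treated as missing unless a section says otherwise. Sections 4.3.2.3.1 and 4.3.2.5 do not say otherwise. This is an inference from the text, since the SAP never states it for these endpoints.

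**How many visits?** The analysis visits after Day 1 in SAP Table 3-1 are Days 2, 3, 8, 11, 15, 21, 29, 45 and 60: nine in all, seven of them up to Day 29. The Day 8 window is Days 6–9. For a subject who dies on Day 9:

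- respiratory progression (to Day 29): Days 11, 15, 21 and 29 remain, 4 of 7;
- oxygen/ventilation (to Day 60): Days 11, 15, 21, 29, 45 and 60 remain, 6 of 9.

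**What does one miscoded death do?** About 50 subjects randomized 1:1 give 25 per arm.

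- Against counting death as failure: 1/25 = 4 percentage points at that visit. For an assumed 1 to 6 deaths in an arm, all coded off support, the range is 4 to 24 points. This is a ceiling.
- Against leaving the subject out after death: with s of the 24 survivors on support, s/24 − s/25 = s/600. For an assumed s = 6 that is 1 point.

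**How often would a death be coded off support?** The documents give no mortality or support rates, so this can only be illustrated. The imputation was imitated for one arm of 25 over 25 simulated arms (625 subjects), with 5 donors, the median of 30 imputations (the SAP uses 100), and death as the only cause of missing data. Three sets of assumed death and recovery rates gave mortality of 43/625 = 6.9%, 70/625 = 11.2% and 143/625 = 22.9% by Day 29. The last set also had slow recovery. The share of post-death values whose median was no support was:

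| Visit | 6.9% mortality | 11.2% mortality | 22.9% mortality, slow recovery |
|---|---|---|---|
| Day 3 | 0% | 0% | 0% |
| Day 8 | 15% | 22% | 14% |
| Day 11 | 35% | 42% | 16% |
| Day 15 | 68% | 61% | 21% |
| Day 21 | 87% | 78% | 44% |
| Day 29 | 86% | 83% | 50% |

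The Day 3 row rests on 4, 1 and 15 values and carries little weight by itself.

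Multiplying mortality by the share at Day 29 gives the shift in one arm's frequency relative to counting death as failure: 6.9% × 0.86 ≈ 6 points, 11.2% × 0.83 ≈ 9 points and 22.9% × 0.50 ≈ 11 points. At Day 8 the same product is below 1 point (for example 23/625 × 0.22 ≈ 0.8). These are shifts within one arm. The treatment comparison moves only as far as deaths, or their coding, differ between arms.

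**The case against.** Several objections have force.

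- **The SAP does not say that deaths are scored as needing no support.** A reader might infer this, but it does not follow. Matching uses the subject's earlier values and severity, so a subject last seen on support often draws donors still on support; in the runs above no Day 3 value was coded off support. A simpler calculation with five unmatched donors gives probabilities of 0.99, 0.94 and 0.83 of being coded off support when 10%, 20% or 30% of donors need support. The same calculation gives 0.50, 0.17 and 0.01 at 50%, 70% and 90%, so its lower range alone would mislead. This objection stands.
- **Another rule might govern.** SAP 4.3.2.3 says that the analyses under it follow the method for time to clinical recovery. That method brings in the censoring rules of 4.3.1, where subjects who die are censored at Day 29. But censoring has no role in a repeated yes/no model. The cross-reference adds ambiguity and does not supply a usable death rule.
- **The sponsor did think about death.** The rule in 4.3.2.1.1 shows this. It also shows that two different approaches are in use and that neither is extended to these endpoints.
- **The stakes are limited.** Support recorded before death stays in the data. Death is the worst category at Day 15, mortality is analysed separately (4.3.2.7), and SAP 3.2 makes p-values other than the primary one descriptive. All of this stands.
- **A while-alive analysis is as legitimate as a composite with death.** This also stands, and the fix leaves that choice to the sponsor.

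**Conclusion.** The point holds as a defect in the missing-data rule. SAP 3.10.1, read literally, imputes respiratory progression and oxygen/ventilation status after death from living subjects in the same arm. This can code some deaths as off support, mainly at later visits. The size is about 4 percentage points per death so coded, at a given visit, relative to death as failure. On the assumed rates this came to roughly 6 to 11 points in one arm at Day 29 and under 1 point at Day 8.

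The conclusion rests on reading post-death status as missing, which 4.3.2.1 supports but the SAP does not state for these endpoints. The frequencies rest on assumed mortality, support and recovery rates.

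A reader might go further and infer that a survival benefit would reverse the oxygen/ventilation comparison. The documents do not support that: they give no rates from which to derive it, and no treatment contrast was simulated here.

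**What to change.** 1. In SAP 3.10.1, state that values after death are not imputed for any secondary endpoint, and restrict missing-at-random imputation to subjects not known to have died.
2. In SAP 4.3.2.3.1 and 4.3.2.5, name one death strategy: either count death as failure from the date of death and label the endpoint a composite, or leave out visits after death, as 4.3.2.1.1 already does, and report the result alongside mortality.
3. Run the other strategy as a sensitivity analysis. Protocol 9.6 already names worst-value assignment, so the composite version is within what was planned.

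The cost is SAP wording and one additional run for each endpoint. The downside is that the result must be labelled as a composite or a while-alive measure and read as such. The sample size of 50 rests on the primary endpoint only, so neither it nor the primary analysis is affected.
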